## **7.6. Incremental cardiopulmonary exercise test**

Exercise testing is increasingly used to evaluate the level of exercise intolerance in patients with lung and heart diseases (9). Patients will undergo cycle ergometry cardiopulmonary exercise testing (CPX) following a ramp protocol (Jaeger Masterscreen CPX) according to ATS guidelines (10). Using CPX, we can extract effort-independent data from exercise. Endpoints taken from CPX will include  $\text{VO}_2$  at peak and anaerobic threshold,  $\text{VE}/\text{VCO}_2$  slope,  $\text{VE}/\text{VCO}_2$  equivalents at metabolic threshold,  $\text{VO}_2/\text{WR}$  slope and  $\text{O}_2$  pulse. All data will be analysed centrally to ensure similar measurement techniques for CPET variables. Details are described in the SPM.

## **7.7. Cardiac Magnetic Resonance (CMR) Imaging**

Cardiac Magnetic Resonance Imaging will be performed at selected centres at Weeks 0, 12 and 24 following a standardised clinical protocol. Patients who are unable to undergo MR scanning will be excluded from this part of the protocol. This may be for reasons such as a metal implant, cardiac arrhythmias or claustrophobia. Using balanced steady state free precession sequences, we will measure right ventricular mass and function. Velocity-encoded sequences will be used to measure the flows through R-sided heart cavities and assess the severity of tricuspid regurgitation. Analysis of the acquired images will be performed using dedicated software. Tracing of epicardial and endocardial borders of SA slices in end-diastole (image phase with the largest cavity area) and endocardial border in end-systole (smallest cavity area) allows calculation of right and left myocardial volume, end-diastolic and end-systolic volumes. From this stroke volume and ejection fraction can be derived. For mass calculation, the myocardial volume is multiplied by the specific density of myocardium (taken as  $1.05 \text{ g/cm}^3$ ). Cardiac output is calculated from the images using the left ventricular stroke volume multiplied by heart rate and cardiac index is then derived by normalization to body surface area. Quantification of right ventricular diastolic function will be made by measuring R-R interval normalised isovolumetric relaxation time on the right two-chamber view, and early peak filling rate (E), atrium-induced peak filling rate (A) on the short-axis images.

A core lab will be established at Hammersmith Hospital to interpret the CMR scans from all sites by CMR trained personnel, blinded to the study timing. Further details are described in the SPM.

## **7.8. Laboratory measurements**

Blood sampling will be performed at each visit to include: NT-pro-BNP as an indicator of cardiac workload; Iron status, as assessed by serum iron, UIBC or TIBC, transferrin saturation, sTfR, ferritin, and hepcidin levels; EPO levels and RDW to assess erythropoiesis. Inflammation status is known to affect hepcidin expression and will be determined by measuring CRP and IL-6 levels. Possible haemolysis will be assessed by measuring unconjugated bilirubin, LDH, haptoglobin and reticulocytes.

### **7.8.1. Type of laboratory**

Central laboratories (see contact details on page 3) will be used to analyse the research bloods. All other routine clinical laboratory parameters (haematology, chemistry, coagulation panel, iron profile) will be analysed by local accredited hospital laboratories. Tests may vary slightly depending on the availability of local hospital assays and so some flexibility with regards to the specific tests will be tolerated e.g. folate or folic acid etc.

Routine clinical laboratory tests include the following:

Haematology	White blood cell count with differential, red blood cell count, platelet count, haemoglobin, hematocrit and reticulocytes, RDW
Standard chemistry	Albumin, Total bilirubin, Unconjugated bilirubin, Urea, Creatinine, Glucose, Total protein, CRP, Urate, Serum electrolytes (Calcium, Chloride, Sodium, Phosphate, Potassium) Bicarbonate, Aspartate aminotransferase (AST); alanine aminotransferase (ALT); $\gamma$ -glutamyl transpeptidase (Gamma-GT); alkaline phosphatase (ALP); lactate dehydrogenase (LDH); creatine kinase (CK) Folic acid and Vitamin B12
Iron profile	Transferrin saturations, ferritin, iron, UIBC/TIBC
Serum pregnancy test	$\beta$ -hCG
Others	EPO

#### 7.8.2. Research samples

Blood samples to measure circulating factors including sTfR, IL-6, Hepcidin, NT pro-BNP haptoglobin, and GDF-15 will be taken at Baseline and Weeks 12 and 24 for research purposes.

Detailed instructions for the preparation, labeling, storage and shipment of the samples can be found in the laboratory manual.

Two additional research blood samples (25ml each) will be collected by the Royal Hallamshire Hospital site only at Week 0 (baseline) and week 12. This is to enable the isolation and study of neutrophil and peripheral blood mononuclear cell function (apoptosis, respiratory burst, phagocytosis, chemotaxis, bacterial killing, integrin expression) and expression (mRNA and protein) in response to iron loading. Patients at this site will be given the option to opt out of these extra blood collections if they wish.

#### 7.8.3. Volume of Blood Collection

The approximate blood volume collected from each individual during the study will be as follows:

Assessment	mL/Collection	Number of Collections	Total (mL)
Clinical chemistry	10	7	70.0
Haematology	3.0	7	21.0
Serum pregnancy test*	1.5	2	3.0
Research blood	15.0	6	90.0
	25.0**	2**	50.0**
	Total blood volume :		184.0mL 234.0mL**

\* for women of childbearing potential

\*\* 2 extra research blood collections (25ml each) will be performed at Weeks 0 and 12 of study participation to freshly isolate human neutrophils and peripheral blood mononuclear cells for functional and expression studies at the Royal Hallamshire Hospital, Sheffield. The total volume of extra blood collection by this site will be 50 ml. Patients at this site will be given the option to opt out of these extra blood collections if they wish.

## 7.9. Quality of Life

CAMPHOR is a disease-specific patient-reported outcome instrument which has been developed for patients with pulmonary hypertension (11). It is sensitive to small changes in health and quality of life in this patient group. It will be collected on Baseline, Week 12 and on Week 24.

## 7.10. Patient Global Assessment

The self-reported Patient Global Assessment will be used at Weeks 2, 12, 14 and 24 to assess patient-perceived response to the intervention.

# 8. PHARMACOVIGILANCE

## 8.1. Definitions

**Adverse Event (AE):** any untoward medical occurrence in a patient or clinical trial subject administered a medicinal product and which does not necessarily have a causal relationship with this treatment. *An AE can therefore be any unfavourable and unintended sign (including an abnormal laboratory finding), symptom, or disease temporally associated with the use of an investigational medicinal product (IMP), whether or not considered related to the IMP.*

**Adverse Reaction (AR):** all untoward and unintended responses to an IMP related to any dose administered. *All AEs judged by either the reporting investigator or the sponsor as having reasonable causal relationship to a medicinal product qualify as adverse reactions. The expression reasonable causal relationship means to convey in general that there is evidence or argument to suggest a causal relationship.*

**Unexpected Adverse Reaction:** an AR, the nature or severity of which is not consistent with the applicable product information (e.g. investigator's brochure for an unapproved investigational product or summary of product characteristics (SmPC) for an authorised product). *When the outcome of the adverse reaction is not consistent with the applicable product information this adverse reaction should be considered as unexpected. Side effects documented in the SmPC which occur in a more severe form than anticipated are also considered to be unexpected.*

**Serious Adverse Event (SAE) or Serious Adverse Reaction (SAR):** any untoward medical occurrence or effect that at any dose:

- Results in death
- Is life-threatening
- Requires hospitalisation, or prolongation of existing inpatients' hospitalisation
- Results in persistent or significant disability or incapacity
- Is a congenital anomaly or birth defect

Medical judgement should be exercised in deciding whether an AE/AR is serious in other situations. Important AE/ARs that are not immediately life-threatening or do not result in death or hospitalisation but may jeopardise the subject or may require intervention to prevent one of the other outcomes listed in the definition above, should also be considered serious.

**Suspected Unexpected Serious Adverse Reaction (SUSAR):** any suspected adverse reaction related to an IMP that is both unexpected and serious.

## 8.2. Assigning Causality

Each adverse event must be assessed by the investigator as to whether or not there is a reasonable possibility of a causal relationship to the study drug. The assignment of the causality should be made by the investigator responsible for the care of the participant using the definitions below. If any doubt about the causality exists the local investigator should inform the study coordination centre who will notify the Chief Investigator. Vifor Pharma and/or other clinicians may be asked to advise in some cases.

In the case of discrepant views on causality between the investigator and others, all parties will discuss the case. In the event that no agreement is made, REC/Regulatory Authority will be informed of both points of view.

### 8.2.1. Causality Description

**Unrelated:** There is no evidence of any causal relationship

**Unlikely:** There is little evidence to suggest there is a causal relationship (e.g. the event did not occur within a reasonable time after administration of the trial medication). There is another reasonable explanation for the event (e.g. the participant's clinical condition, other concomitant treatment).

**Possible:** There is some evidence to suggest a causal relationship (e.g. because the event occurs within a reasonable time after administration of the trial medication). However, the influence of other factors may have contributed to the event (e.g. the participant's clinical condition, other concomitant treatments).

**Probable:** There is evidence to suggest a causal relationship and the influence of other factors is unlikely.

**Definitely:** There is clear evidence to suggest a causal relationship and other possible contributing factors can be ruled out.

### Not assessable:

There is insufficient or incomplete evidence to make a clinical judgment of the causal relationship.

## 8.3. Assigning Severity

For each AE intensity should be defined according to the following criteria:

- **Mild:** Awareness of sign or symptom, but easily tolerated.
- **Moderate:** Discomfort enough to cause interference with normal daily activities.
- **Severe:** Inability to perform normal daily activities.
- **Life threatening or disabling:** Immediate risk of death from the reaction as it occurred.
- **Death:** The event resulted in death.

## **8.4. Adverse event reporting procedures**

### **8.4.1. Screening period**

All adverse events should be documented. SAEs occurring between signing the Informed Consent Form and study drug initiation are only required to be reported if they are considered by the investigator to be related to study-mandated procedures.

### **8.4.2. Treatment period**

All adverse events should be documented. Depending on the nature of the event the reporting procedures below should be followed. Any questions concerning adverse event reporting should be directed to the study coordination centre in the first instance.

#### **8.4.2.1. Non serious AR/AEs**

All such toxicities, whether expected or not, should be recorded in the Adverse Events section of the case report form.

#### **8.4.2.2. Serious AR/AEs**

All SAEs must be reported to the study coordination centre within 24 hours of the investigator being made aware of the event. The investigator should complete the SAE form and send it to the study coordination centre together with relevant treatment forms and anonymised copies of all relevant investigations. Follow up information about a previously reported SAE must be reported within 24 hours of receiving it.

However relapse and death due to pulmonary hypertension, and hospitalisations for elective treatment of a pre-existing condition do not need reporting as SAEs.

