### **6.2. Baseline/Randomisation Visit (Week 0)**

The patient will be admitted to the research unit for up to 3 days in order to undergo the following procedures:

- Physical examination
- Concomitant medications
- Document adverse events
- ECG
- Research blood sampling (NT pro-BNP, IL-6, hepcidin, sTfR and EPO). Neutrophil and peripheral blood mononuclear cell function and expression (Sheffield site only)
- Fasting glucose and insulin
- Incremental Cardiopulmonary Exercise Test
- Endurance Cardiopulmonary Exercise Test
- CAMPHOR questionnaire
- Cardiac MRI

Following completion of the above procedures, the patient will be randomised and receive an infusion of either the study drug (Ferinject®) or placebo (saline).

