### **6.4. Week 12 (+/- 3 days)**

The patient will be admitted to the research unit for up to 3 days in order to undergo the following procedures:

- Physical examination
- Concomitant medications
- Document adverse events
- Vital signs: Resting supine blood pressure (BP), pulse measurement, temperature, pulse oximetry and weight
- ECG
- Modified NYHA/WHO Functional Class
- 6MWT and Borg dyspnoea index

- Blood samples for routine haematology, blood chemistry, (including iron indices), and serum pregnancy test (woman of childbearing potential only)
- Research blood sampling (NT pro-BNP, IL-6, hepcidin, sTfR and EPO; neutrophil and peripheral blood mononuclear cell function and expression (Sheffield site only)
- Fasting glucose and insulin (taken after an overnight stay and before dosing)
- Incremental Cardiopulmonary Exercise Test
- Endurance Cardiopulmonary Exercise Test
- Cardiac MRI (where the facility is available)
- CAMPHOR questionnaire
- Patient Global Assessment (PGA)

Following completion of the above procedures, the patient will be administered either the study drug (Ferinject®) or placebo (saline).

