## **8.6. Reporting to the Sponsor**

All SAEs and SUSARs must be forwarded the Imperial College Joint Research Office within 24 hours of the Investigator learning of its occurrence.

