## **8.7. Reporting to Vifor Pharma Drug Safety**

All SAEs that are considered possibly, probably or definitely related to the study drug must be forwarded to Vifor Pharma Pharmacovigilance by fax or e-mail within 1 business day of learning of the event:

[contact]  
[[contact]](mailto:[contact])

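### Section 8.4.2.2 exempts PH relapse and PH death from SAE reporting even when the event is also attributed to study drug or a study procedure, in conflict with 8.6 and 8.4.1

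*Protocol*

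**What the plan says.** Section 8.4.2 requires all adverse events in the treatment period to be documented. Section 8.4.2.2 sets a 24-hour limit for reporting SAEs to the coordination centre and then carves out a class: "However relapse and death due to pulmonary hypertension, and hospitalisations for elective treatment of a pre-existing condition do not need reporting as SAEs". The carve-out has no condition about study drug or study procedures, and the protocol does not define relapse.

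For the time between consent and study drug initiation, section 8.4.1 has a different rule. SAEs are "only required to be reported if they are considered by the investigator to be related to study-mandated procedures". PH is not mentioned there.

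Three later sections bear on the point. Section 8.2 asks the investigator to judge "whether or not there is a reasonable possibility of a causal relationship to the study drug". Section 8.6 states "All SAEs and SUSARs must be forwarded the Imperial College Joint Research Office within 24 hours". Section 8.7 concerns the manufacturer: "All SAEs that are considered possibly, probably or definitely related to the study drug must be forwarded".

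The incremental and endurance exercise tests are done at Weeks 0, 12 and 24. At Week 0 they come before the first infusion ("Following completion of the above procedures, the patient will be randomised and receive an infusion of either the study drug", section 6.2). At Week 12 they come before the second ("Following completion of the above procedures, the patient will be administered either the study drug", section 6.4). Under section 7.4 the endurance test continues to the patient's limit.

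**The concern.** Exempting the natural course of the disease from expedited reporting is a reasonable choice. The difficulty is that the test for exemption is cause by PH alone, while a serious event in this trial may have more than one cause. Right heart failure or death after an exercise test to the limit could be put down to both PH and the test. In that case 8.4.2.2 can be read as removing the duty to report, and the causality question in 8.2 does not ask about the test.

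At stake is prompt central knowledge. The study runs in 5 centres, adverse events are a listed secondary outcome, and section 11.6 lets the Chief Investigator end the trial. A run of such events across sites is noticed sooner if each is notified within 24 hours and carries a recorded judgement on the procedure.

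**Working it through.** No figure in the protocol bears on this point, so the check sets the reporting rules against the visit schedule. Study drug initiation in 8.4.1 is taken to mean the first infusion, active or saline, since blinded staff could apply no other reading.

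**Step 1: which rule covers which test.** A Week 0 test precedes the first infusion. An event with onset before that infusion falls under 8.4.1. An event caused by a Week 0 test but starting after the infusion falls under 8.4.2.2. Events from the Week 12 and Week 24 tests all fall under 8.4.2.2.

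**Step 2: outcome by attribution.**

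| Serious event (relapse or death where PH is involved) attributed to | Onset before first infusion (8.4.1) | Onset after first infusion (8.4.2.2) |
|---|---|---|
| PH alone | Not reportable | Exempt |
| Exercise test alone | Reportable | Reportable |
| PH and exercise test | Reportable | Can be read as exempt |
| PH and study drug | Does not arise | Can be read as exempt, but see step 3 |

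Only the third row changes across dosing, and the protocol gives no reason for the change.

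**Step 3: whether another section restores the duty.**
- 8.6 covers all SAEs, and 8.1 defines an SAE by its outcome, so a PH death meets the definition. Taken literally, 8.6 requires 24-hour notice to the sponsor and so contradicts 8.4.2.2. The protocol does not say which prevails.
- 8.5 also speaks of all SAEs and SUSARs, but leaves the terms to local regulatory guidelines.
- 8.5 on SUSARs and 8.7 carry no PH exemption, so they pull a drug-related event back into reporting. Neither covers an event related only to a procedure.
- 8.2 records causality to study drug only, so relatedness to an exercise test need not be recorded after dosing.

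For drug-related events there are therefore conflicting instructions. For procedure-related PH events after dosing, 8.6 is the only specific route, and it is the one in conflict with the exemption.

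**The case against.** The strongest reply is that the protocol already brings these events to central attention. All adverse events are documented. Section 8.4.2 directs reporting questions to the coordination centre, and 8.2 sends doubts about causality there and on to the Chief Investigator. Section 8.6 contains no exemption. It can also be said that heart failure provoked by a test is not obviously a relapse and is due to the test, so the exemption would not apply.

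Much of this stands, and it confines the point to mixed-cause events and to expedited notice. It does not remove it. The query routes have no 24-hour limit, and the one in 8.2 is framed around study drug. A site that reads a plain exemption has little reason to ask. Section 8.6 cannot safely be taken at face value either: applied literally it would also cancel the limit in 8.4.1, so a site may well take it to mean SAEs that are otherwise reportable. Because relapse is undefined, the text does not settle whether the example is covered.

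Three stronger readings are tempting, and the documents do not support them.
- A reader might infer that the drug-related routes would miss events at Weeks 12 and 24, because 8.2.1 illustrates an unlikely relation with the case where "the event did not occur within a reasonable time after administration of the trial medication". But section 4.2 builds the design on exercise data 12 weeks after iron, so the protocol does not treat that interval as too late for a drug effect.
- A reader might call PH decompensation an expected harm of these tests. The protocol gives no frequency, and exclusion 16 removes patients who cannot perform the test, for instance because of syncope.
- A reader might size the gap by counting tests: 60 patients × 2 tests × 2 visits = 240 at Weeks 12 and 24, out of 60 × 2 × 3 = 360. That two-thirds share only restates that two of the three test visits follow dosing. Nor is 240 an upper limit, since section 10 allows recruitment beyond 60.

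**Conclusion.** The point holds in a narrow form. Section 8.4.2.2 lacks a relatedness condition. It conflicts with 8.6 and is out of line with 8.4.1, where a procedure-related SAE with onset before the first infusion is reportable whether or not PH is involved. After dosing, a serious PH event also attributed to an exercise test can be read as exempt from 24-hour reporting, and its relation to the test need not be recorded.

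The gap lies in expedited central notice and in recorded procedure-relatedness, not in whether the event is documented. An event put down to the test alone stays reportable, and one put down to PH alone was not reportable before dosing either. No event rate can be derived, so the size is left open. The conclusion assumes that an investigator may attribute one event to both PH and a test, and may apply the exemption as written. The change is worth making because the rule concerns deaths and serious deterioration and is cheap to correct. The estimates of treatment effect on exercise capacity are not affected.

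**What to change.** 1. In 8.4.2.2, limit the exemption to PH relapse or PH death that the investigator judges unrelated to both study drug and study-mandated procedures. All others are reported within 24 hours.
2. In 8.6, state whether events exempt under 8.4.2.2 are still forwarded to the sponsor.
3. In 8.2, add an assessment of relatedness to study-mandated procedures, so that the question already asked in 8.4.1 continues through the treatment period.

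Relapse should not be defined by borrowing exclusion 7 (PAH-related admission or change in PAH therapy). That would write every PAH admission judged unrelated into the exempt class, and would bring in therapy changes that are not in themselves serious.

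The cost is wording in three sections, one item on the AE form and a few extra SAE forms, some of which will turn out to describe natural progression. No visit, test or committee is added.

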## **8.5. Reporting to the Regulatory Authorities**

The Sponsor has delegated the responsibility for notifying the Regulatory authority and REC of all SUSARs occurring during the study to the Chief Investigator. All SAEs and SUSARs must be reported in accordance with local regulatory guidelines:

*Life threatening SUSARs should be reported to the RA and REC no later than **7 days** after the CI has first knowledge of the minimum criteria for expedited reporting. Further relevant information should be given within a further 8 days.*

*Non-fatal and non-life threatening SUSARs should be reported to the RA and REC no later than **15 days** after the CI has first knowledge of the minimum criteria for expedited reporting. Further relevant information should be given as soon as possible.*

An annual safety report will be submitted on the anniversary of the Clinical Trial Application to the RA and REC.

